6.2 Additional Study Assessments

6.2.1 Laboratory Assessments

Laboratory analyte samples will be collected throughout the study. A list of these analytes is contained in Appendix B.

6.2.2 Congestive Heart Failure

Any patient that develops signs, symptoms or test results suggestive of new onset or worsening (if pre-existing) congestive heart failure should have the following evaluations performed (in addition to any tests deemed to be necessary by the attending physician) as soon as possible and the Investigator should consider referral to a cardiologist:

- Chest x-ray
- 12 lead ECG
- Echocardiogram

In addition the Congestive Heart Failure supplemental CRF pages should be completed in the eCRF.

6.2.3 *Arrhythmias*

Any patient that develops signs, symptoms or test results suggestive of new cardiac arrhythmia should have the following evaluations performed (in addition to any tests deemed to be necessary by the attending physician) as soon as possible and the Investigator should consider referral to a cardiologist:

- 12 lead ECG
- Echocardiogram

In addition the Arrhythmias supplemental CRF pages should be completed in the eCRF.

6.2.4 *Myocardial Ischemia*

Any patient that develops signs, symptoms or test results suggestive of myocardial ischemia should have the following evaluations performed (in addition to any tests deemed to be necessary by the attending physician) and the Investigator should consider referral to a cardiologist:

- Serial 12 lead ECGs
- Serial cardiac enzyme evaluation (CKMB, cardiac troponin I or cardiac troponin T)

In addition the Myocardial Infarction supplemental CRF pages should be completed in the eCRF.

6.2.5 *Event-Specific Supplemental CRF Pages*

In the event of any of the following, the corresponding supplemental CRF pages should be completed in the eCRF:

- Death
- Valvulopathy (i.e., signs, symptoms or test results suggestive of impairment of function of 1 or more cardiac valves)
- Deep vein thrombosis or pulmonary embolism
- Peripheral arterial thromboembolism
- Cerebrovascular event or transient ischemic attack
- Revascularization
- Pulmonary hypertension

6.3 **Restriction on the Lifestyle of Patients**

6.3.1 *Contraception Requirements*

All patients of childbearing potential must refrain from sperm/egg donation and practice effective contraception from the time of signing the informed consent form until at least 3 months after their last dose of Study Drug.

For the purposes of this study, women of childbearing potential are defined as any female who has experienced menarche, and that does not meet 1 of the following conditions:

- Postmenopausal: 12 months of spontaneous amenorrhea in females > 55 years of age or, in females ≤ 55 years, 12 months of spontaneous amenorrhea without an alternative medical cause and FSH levels in the postmenopausal range for the laboratory involved
- 6 weeks after surgical bilateral oophorectomy with or without hysterectomy
- Post hysterectomy

For the purposes of the study, effective contraception is defined as follows:

For male patients:

1. Effective male contraception includes a vasectomy with negative semen analysis at Follow-up, or the use of condoms together with spermicidal foam/gel/film/cream/suppository. Male patients must also encourage their female partner to use effective contraception from the time of signing the informed consent until 3 months after the patient's last dose of Study Drug. Effective contraceptive for the female partner includes: surgical sterilization (e.g., bilateral tubal ligation), hormonal contraception, intrauterine contraception/device, or barrier methods (female condom*, diaphragm, sponge, cervical cap) together with spermicidal foam/gel/film/cream/suppository. Male patients with partners that are pregnant must use condoms to ensure that the fetus is not exposed to the Study Drug.

For female patients:

2. Using 2 or more of the following acceptable methods of contraception:
 - Surgical sterilization (e.g., bilateral tubal ligation)
 - Hormonal contraception
 - Oral contraceptive (either combined or progestogen alone)
 - Injectable progestogen
 - Implants of etonogestrel or levonorgestrel
 - Percutaneous contraception/device
 - Intrauterine contraception/device
 - Combination of male condom* with female diaphragm together with spermicidal foam/gel/ film/cream/suppository

***Note: A female condom and a male condom should not be used together as friction between the 2 can result in either product failing**

6.3.2 Other Requirements

All patients will be required to fast for at least 8 hours before a blood sample is taken for the pharmacodynamic and retinol assessments.

7. STUDY DRUG

7.1 ISIS 420915 or Placebo

Study Drug (ISIS 420915 or placebo) characteristics are listed in Table 1.

The Study Drug is contained in stoppered glass vials and will be provided to the Study Center by the Sponsor. The Study Drug storage and preparation instructions will be provided by the Sponsor. For long term storage at clinical sites, the Study Drug must be stored securely at 2° to 8° Celsius and be protected from light.

Table 1 Study Drug Characteristics

| Study Drug | ISIS 420915 | Placebo |
|--------------------------------|---|---|
| Strength | 200 mg/mL | NA |
| Volume/Formulation | 1 mL solution per 2 mL vial or 1.5 mL solution per 3 mL vial | 1 mL solution per 2 mL vial or 1.5 mL solution per 3 mL vial |
| Route of Administration | SC 1.5 mL | SC 1.5 mL |

7.2 Packaging and Labeling

The Sponsor will provide the Investigator with packaged Study Drug labeled in accordance with specific country regulatory requirements.

7.3 Study Drug Accountability

The study staff is required to document the receipt, dispensing, and return of Study Drug supplies provided by the Sponsor. The Study Center must return all used and unused Study Drug to the Sponsor or designee.

8. TREATMENT OF PATIENTS

8.1 Study Drug Administration

For each individual patient, Study Drug will be administered subcutaneously as a single 1.5 mL injection 3 times in the first week and then once weekly for Weeks 2-65. For weeks with a clinic visit, Study Drug will be administered at the clinic. For weeks that do not include a clinic visit, Study Drug may be administered by either Study Center personnel or at home by the patient/caregiver. Every effort should be made to ensure the previous week's dose is given 7 days prior to a scheduled clinic visit. If Study Drug is to be administered at home, dosing instructions and training will be provided to the patient by the Study Center personnel.

If needed for tolerability reasons, the single 1.5 mL injection may be administered as 2 noncontiguous injections of smaller volume, but prior discussion with the Study Medical Monitor is encouraged.

Please refer to the Study Drug Manual provided by the Sponsor for more detailed instructions for Study Drug preparation and administration.

8.2 Other Protocol-Required Drugs

All patients will take daily oral supplemental doses of the RDA of vitamin A (approximately 3000 IU vitamin A or the closest approximate dose as available in the region in which the patient resides). Commercially available vitamin A as a single supplement, or as part of a multivitamin, will be provided by the Study Center or designee, in accordance with local regulatory requirements and availability.

8.3 Other Protocol-Required Treatment Procedures

There are no other protocol required treatment procedures.

8.4 Treatment Precautions

There are no specific treatment precautions required for this study.

8.5 Safety Monitoring Rules

Please refer also to the 'Guidance for Investigator' section of the Investigator's Brochure.

In addition to the standard monitoring of clinical safety parameters, the following guidelines are provided for the monitoring of selected parameters chosen based on preclinical and clinical observations.

Confirmation Guidance: At any time during the study (treatment or post-treatment periods), the initial clinical laboratory results meeting the safety monitoring or stopping criteria presented below **must be confirmed** by performing measurements (ideally in the same laboratory that performed the initial measurement) on new specimens. All new specimen collections should take place as soon as possible (ideally within 3 days of the initial collection).

Stopping Rule Guidance: In the event of an initial clinical laboratory result that meets a stopping criterion, patients must not be re-dosed until a confirmatory test result has been reviewed by the Study Medical Monitor. If any of the stopping criteria described below (refer to Sections 8.6.1 to 8.6.3) are met and are confirmed, the patient will be permanently discontinued from further treatment with Study Drug (ISIS 420915 or placebo), evaluated fully as outlined below and in consultation with the Study Medical Monitor or appropriately qualified designee, and will be entered into the post-treatment evaluation portion of the study (after completing the early termination and EOT efficacy assessments). In general, patients who do not meet the stopping rules based upon retest may continue dosing. However, the Investigator and the Study Medical Monitor (or appropriately qualified designee) should confer as to whether additional close monitoring of the patient is appropriate.

Additional Guidance: If possible, a pharmacokinetic sample should be collected as soon as possible after an SAE has occurred (preferably within 2 weeks). In addition, if a patient is asked to return to the clinic for additional evaluations due to an AE, then a pharmacokinetic sample should be taken at the time of the unscheduled visit.

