8.5.3 Safety Monitoring Rules for Ocular Effects

All patients should receive an ophthalmology examination by an eye specialist at Baseline, after approximately 7 months of receiving Study Drug (Week 29) and also at the end of the dosing period (Week 65). An ERG will also be performed at Baseline and the end of the dosing period (Week 65). In addition, any patient that complains of persistent ocular symptoms compatible with vitamin A deficiency (e.g., night blindness or dry eyes) should be referred for an ophthalmology examination. If the ophthalmologist confirms the patient's symptoms are consistent with vitamin A deficiency and/or the examination reveals physical findings that are consistent with vitamin A deficiency (but do not reach the stopping rule criteria described in Section 8.6.4) then an ERG examination should be conducted and analyzed by the central reader. In addition, it is suggested that a review of diet and supplement use and an evaluation for factors which may contribute to low vitamin A levels such as infection, alcohol consumption, and zinc and/or iron deficiency be conducted.

If the ERG is changed from baseline and shows clear signs of vitamin A deficiency as assessed by the central reader and described below, then the patient should be monitored more frequently. Frequency will be determined by the Sponsor Medical Monitor in consultation with the Investigator and ophthalmologist.

Clear signs of vitamin A deficiency as assessed by ERG include:

- a) Changes from baseline > 50%, and
- b) Values below normal range (if baseline values were within normal range), and
- c) Changes that are approximately symmetrical between eyes (unless there is an alternative explanation for asymmetry)

Dosing with Study Drug may continue while these evaluations are being performed.

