8.5.4 Safety Monitoring Rules for Platelet Count Results

Platelets will be monitored weekly throughout the treatment period and for a minimum of 6 weeks after the last dose of Study Drug (this includes early termination patients as well as patients that complete the full 65-week treatment period). For patients participating in the Post-Treatment Evaluation Period, frequency of testing after the Week 71 visit will be determined by the Investigator in consultation with the Study Medical Monitor. For patients participating in the ISIS 420915-CS3 study, weekly monitoring should continue between the last dose of Study Drug in CS2 and first dose of Study Drug in CS3. If this period extends beyond 6 weeks, the frequency of monitoring will be determined by the Study Medical Monitor.

All platelet count results must be promptly reviewed by the Investigator to ensure that the count has not met the stopping rule.

If for any reason there is more than 14 days between platelet values (e.g., lab report of an unreadable sample due to clumping, hemolysis, or quantity not sufficient, or a missed lab assessment), the Investigator will contact the patient to hold dosing until a new platelet value is obtained and reviewed.

If a patient's platelet counts fall below $100,000/\text{mm}^3$, additional lab tests may be requested as determined by the Investigator in consultation with the Study Medical Monitor.

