8.6.3 Stopping Rule for Platelet Count Results

In the event of a confirmed platelet count less than 75,000/mm³, and in the presence of major bleeding or clinically-relevant non-major bleeding (defined below; Schulman et al. 2005), dosing of a patient with Study Drug (ISIS 420915 or placebo) will be stopped permanently. The follow-up schedule for any events meeting this stopping criterion will be determined by the Investigator in consultation with the Study Medical Monitor.

In the event of a confirmed platelet count less than 75,000/mm³, and in the absence of major bleeding or clinically-relevant non-major bleeding, further dosing of a patient with Study Drug (ISIS 420915 or placebo) must be held until the platelet count returns to at least 100,000/mm³. Weekly platelet monitoring should continue during this period. In addition, the Investigator should give consideration to collecting duplicate platelet samples for study in a local lab in parallel to the central lab if it would provide quicker access to the patients platelet count. If the platelet count was confirmed to be < 50,000/mm³, then monitoring should be increased to daily until two successive values show improvement. The Investigator must notify the Study Medical Monitor within 24 hours of any local lab platelet results that show a level < 50,000/mm³.

The suitability of the patient for continued dosing and the need for any modification to treatment schedule or dose (refer to Section 8.7) will be determined by the Investigator in consultation with the Study Medical Monitor and will be based on factors such as the original rate of decline in the patient's platelet count, whether any bleeding events were experienced by the patient, and the speed of recovery of platelet count upon holding of dosing.

Definition major bleeding events:

International Society on Thrombosis and Haemostasis (ISTH) Major Bleeding:

1. Fatal bleeding, and/or
2. Symptomatic bleeding in a critical area or organ, such as intracranial, intraspinal, intraocular, retroperitoneal, intraarticular or pericardial, or intramuscular with compartment syndrome, and/or
3. Bleeding causing a fall in hemoglobin level of 20 g/L (1.24 mmol/L) or more within 24 hours, or leading to transfusion of 2 or more units of whole blood or red cells

Definition clinically-relevant, non-major bleeding events:

1. Multiple-source bleeding
2. Spontaneous hematoma > 25 cm²
3. Excessive wound hematoma (not injection site related)

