8.8 Discontinuation of Study Treatment

A patient must permanently discontinue study treatment for any of the following:

- The patient becomes pregnant. Report the pregnancy according to instructions in Section 9.5.4
- The patient withdraws consent
- The patient experiences an adverse event that necessitates permanent discontinuation of study treatment
- The patient develops laboratory test abnormalities that meet any of the stopping rules listed in Section 8.6
- The patient experiences an AE that necessitates unblinding of the Investigator to the patient's treatment assignment

The reason for discontinuation of study treatment must be recorded in the CRF and source documentation.

Patients that discontinue from treatment are encouraged to remain in the study. Every effort should be made to complete the early termination visit and the EOT efficacy assessment followed by all post-treatment evaluation visits. If the patient declines to participate in the post-treatment evaluation visits, at a minimum, the early termination visit and EOT efficacy assessment procedures should be performed at the time of withdrawal (See Appendix A) and ideally within 14 days from the last dose of Study Drug. If early termination assessments are to be performed on a day with mNIS+7 EOT assessment, the mNIS+7 assessment should be performed first.

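### Protocol 8.5 and 8.8 require permanent discontinuation without exempting the no-bleeding platelet tier of 8.6.3, which orders only a dosing hold with possible resumption

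*Protocol*

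**What the plan says.** **Protocol 8.5, Stopping Rule Guidance**, has two consecutive sentences that use the same term.

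- Before confirmation, the instruction covers any "initial clinical laboratory result that meets a stopping criterion, patients must not be re-dosed until a confirmatory test result has been reviewed"; the reviewer is the Study Medical Monitor.
- After confirmation: if any stopping criteria in 8.6.1 to 8.6.3 "are met and are confirmed, the patient will be permanently discontinued from further treatment with Study Drug". The reference to 8.6.1 to 8.6.3 takes in the platelet section.

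**Protocol 8.8** lists the events for which treatment must end permanently. One of them is: "The patient develops laboratory test abnormalities that meet any of the stopping rules listed in Section 8.6".

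**Protocol 8.6.3**, headed as the stopping rule for platelet counts, has two tiers, both for a confirmed count below 75,000/mm³.

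- With major or clinically relevant non-major bleeding, dosing stops permanently. The paragraph adds: "The follow-up schedule for any events meeting this stopping criterion will be determined by the Investigator".
- Where such bleeding is absent, "further dosing of a patient with Study Drug (ISIS 420915 or placebo) must be held until the platelet count returns to at least" the recovery threshold of 100,000/mm³. A later paragraph deals with what follows: "The suitability of the patient for continued dosing and the need for any modification to treatment schedule or dose" is decided by the Investigator with the Study Medical Monitor.

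**Protocol 8.7** allows up to 2 schedule adjustments. It gives a count below 75,000/mm³ under 8.6.3 as its example and permits a cautious return to the original regimen.

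**Protocol 8.5.4** asks the Investigator to review every platelet count promptly "to ensure that the count has not met the stopping rule".

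**The concern.** Sections 8.5 and 8.8 are mandatory and unqualified, and their scope includes 8.6.3. A site that works from either section alone would end treatment for a patient with a confirmed low count and no bleeding. A site that works from 8.6.3 would hold dosing, wait for recovery, and might resume. Two sites following the protocol could therefore treat the same patient differently, and one of the two courses cannot be reversed within the study.

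This rule in particular should have a single reading. The statement of purpose for Amendment 9 reports one recent case of severe thrombocytopenia in this study and two earlier ones, 1 + 2 = 3 in all, one with a fatal intracranial bleed. That is context for the importance of the rule. It does not count patients affected by the conflict.

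**Working it through.** The plan gives no figure to reproduce, and the point rests on no sample size, power or event rate. The check is a comparison of the texts.

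**Step 1. What each criterion orders in its own section**

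| Section | Criteria | Order in that section |
|---|---|---|
| 8.6.1 liver | 4 | permanent stop, absent an alternative explanation |
| 8.6.2 renal (24-hour urine) | 3 | permanent stop, absent an alternative explanation |
| 8.6.3 platelets, with bleeding | 1 | permanent stop |
| 8.6.3 platelets, no bleeding | 1 | hold to at least 100,000/mm³, then decide |

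Total 4 + 3 + 1 + 1 = 9. Eight order a permanent stop and one orders a hold. The general sentence in 8.5 fits the first eight and not the ninth.

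**Step 2. One patient under each reading**

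Take a count below 75,000/mm³ without bleeding.

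*Reading A: the no-bleeding tier is a stopping criterion.*
- Initial count: 8.5 bars re-dosing until the retest has been reviewed.
- Confirmed count: 8.5 and 8.8 require a permanent stop, while 8.6.3 requires a hold and allows resumption. The orders contradict each other.

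*Reading B: only the bleeding tier is a stopping criterion.*
- Confirmed count: 8.6.3 governs and the contradiction with 8.5 goes away. Section 8.8 remains awkward, because it speaks of stopping rules in 8.6 and the heading of 8.6.3 covers both tiers.
- Initial count: the bar in 8.5 uses the same term, so it no longer clearly reaches this patient, and the hold in 8.6.3 is worded for a confirmed count.

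**Step 3. What follows**

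The evident intent is to withhold dosing on the first low count, hold if it is confirmed without bleeding, and allow resumption after recovery. To obtain that from the text, the term *stopping criterion* must include the no-bleeding tier in the first sentence of 8.5 and exclude it in the next. No consistent use of the term gives the intended rule. A repair that only exempts the tier from the permanent stop would invite Reading B, so the initial-count instruction has to be stated alongside it.

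**The case against.** **The specific rule governs the general one.** The provisions on resumption in 8.6.3 and on schedule adjustment in 8.7 would be pointless if 8.5 ended treatment. The phrase *this stopping criterion* appears in 8.6.3 only in the bleeding paragraph. The heading is weak evidence, since 8.6.5 is also headed as a stopping rule and requires only repeat ECGs and discussion. As evidence of intent this stands. But the protocol states no order of precedence, and 8.5 cites 8.6.3 by number.

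**A wrongful stop is unlikely in practice.** The Study Medical Monitor reviews the confirmatory result and shares the decision on continued dosing. That stands and lowers the likelihood of harm. It does not remove the conflict.

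**A literal reading proves too much.** The liver and renal rules stop dosing only without an alternative explanation, and 8.5 and 8.8 do not repeat that condition. This is fair as a warning against resting much on the count of nine. The cases still differ in kind: the liver and renal condition decides whether the rule is triggered, and once triggered the order is the same permanent stop. In the no-bleeding platelet tier the order itself is different.

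**The text already gives a workable sequence.** The bar in 8.5 concerns a laboratory result, and the only laboratory element of the platelet rule is the count. So an initial low count bars dosing, confirmation with bleeding means a permanent stop, and confirmation without bleeding means a hold. The first step is indeed the most natural reading. But treating the count alone as the stopping criterion in that step also triggers the permanent stop in the next sentence of 8.5 once the count is confirmed.

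**Conclusion.** Sections 8.5 and 8.8 are wrong as written. For a confirmed count below 75,000/mm³ without major or clinically relevant non-major bleeding they order a permanent stop, and 8.6.3 with 8.7 orders a hold with possible resumption. It affects one of the two platelet tiers, the only one of nine criteria whose own section orders a hold. The number of patients in that tier is not given, so no frequency can be put on it. The conclusion assumes that the Investigator's Brochure section cited in 8.5 and the Safety Management Plan cited in 9.1, neither available here, do not set a precedence. Even if they do, the protocol's own mandatory sentences should agree.

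Three stronger inferences are tempting and are not supported.

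- **That sites may dose on an unconfirmed low count.** A reader might infer this from the word *confirmed* in 8.6.3. But 8.5 bars re-dosing on an initial laboratory result, and 8.5.4 treats the count itself as able to meet the rule. Where the protocol allows dosing to go on during evaluation, it says so, as in 8.5.3 ("Dosing with Study Drug may continue while these evaluations are being performed") and in item 2 of 8.6.1. Section 8.6.3 has no such permission.
- **That the conflict materially damages the primary analysis.** SAP 3.2.1.3 excludes efficacy assessments more than 52 days after the last dose, so a permanent stop can cost a Week 66 value. That holds for any early stop, and nothing shows how many patients would be lost through this conflict. The multiple-imputation analyses in SAP 3.3.3.2 also include in-window assessments beyond 52 days.
- **That the SAP tabulation is defective.** SAP 3.9.4 counts patients who stopped treatment because of a rule, and SAP 3.2.3 tabulates reasons for dose pauses. A separate line for patients held and not restarted would be a reporting preference.

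**What to change.** - In **8.5 and 8.8**, add: *except a confirmed platelet count below 75,000/mm³ without major or clinically relevant non-major bleeding, which follows the dosing hold in 8.6.3*.
- In **8.6.3**, state that any initial count below 75,000/mm³ suspends dosing until the Study Medical Monitor has reviewed the confirmatory result. This keeps the bar in 8.5 intact once the exception is in place.
- In **8.5.4**, refer to *the hold or stopping criteria in 8.6.3*.

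The cost is a short wording amendment and a clarification letter to sites. An occasional weekly dose would be delayed by a few days when the low count is not confirmed, a delay that the most natural reading of 8.5 already implies. No change to the SAP is needed.
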